**Table 3. Primary AE Safety Endpoint Definitions**

Primary Adverse Event	Description/Criteria
Death	Death
Myocardial infarction (MI)	Myocardial infarction will be demonstrated by any one of the following: 1) detection of ECG changes indicative of new ischemia (new ST-T wave changes or new LBB) that persist for more than 1 hour. 2) development of new pathological Q waves on an ECG 3) imaging evidence of new loss of viable myocardium or new regional wall motion abnormality
Persistent diaphragmatic paralysis	Change in baseline diaphragmatic function as evidenced by elevation of the diaphragm above the normal range but not due to a pulmonary process such as atelectasis.
Stroke or transient ischemic attack (TIA)	Stroke is an acute symptomatic episode of neurological dysfunction attributed to a vascular cause (ischemia or hemorrhage) in which symptoms last more than 24 hours, or if symptoms last less than 24 hours, a brain imaging study demonstrates infarction.  Transient ischemic attack is a new focal neurological deficit with rapid symptom resolution always within 24 hours.
Peripheral or organ thromboembolism	Formation in a blood vessel of a clot (thrombus) that results from the breaking loose of all or part of an existing thrombus, which is then carried by the blood to lodge in/occlude a more distal vascular site.
Pericarditis	Inflammation of the pericardial space that results in an effusion that leads to hemodynamic compromise or required pericardiocentesis, prolongs hospitalization by more than 48 hours, requires hospitalization, or persists for more than 30 days following the ablation procedure.
Cardiac tamponade/perforation	The development of a significant pericardial effusion during or within 30 days of undergoing the index AF ablation procedure. A significant pericardial effusion is one which results in hemodynamic compromised (<80mmHg systolic bp), requires elective or urgent pericardiocentesis, or results in a 1cm or more pericardial effusion as documented by echocardiography.
Vascular access complications	Vascular access complication (e.g. groin hematoma, AV fistula, pseudoaneurysm) requiring intervention (e.g. surgical repair, blood transfusion) or admission or prolonged hospitalization.
Hospitalization (initial or prolonged)	*excludes hospitalization (initial or prolonged) solely due to arrhythmia (AF/AFL/AT) recurrence

Primary Adverse Event	Description/Criteria
	or due to non-urgent cardioversion (pharmacological or electrical)
Heart block	Impairment of AV conduction requiring intervention due to inappropriate ablation application.
Pulmonary vein (PV) stenosis	>70% diameter reduction of pulmonary vein from baseline CT/MRA scan.
Atrio-esophageal fistula	Connection between the atrium and the lumen of the esophagus as evidenced by documentation of esophageal erosion combined with evidence of a fistulous connection to the atrium.

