**FARAPULSE PEFCAT Clinical Study (same as subject investigation)**

FARAPULSE, Inc, has also initiated a safety and feasibility study at Na Homolce Hospital in Prague, Czech Republic under the “PEFCAT” Protocol, CS0267. This safety and feasibility study is the same investigation that is being proposed for Pessac, France. This study is being conducted using the FARAPULSE Endocardial Ablation System; the same system which will be used in the subject investigation. Sixteen (16) patients have been enrolled at Na Homolce between October and November of 2018. All patients were discharged in good condition. One patient was treated for an air embolism during the index procedure. This event was resolved.. At the conclusion of the index procedure all pulmonary veins (PVs) were isolated using the FARAPULSE device.

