### 3.5 Complications of Catheter Based and Surgical Ablation

The risks and complications associated with thermal or non-thermal cardiac ablation depend on the complexity of the procedure. The most common complications due to cardiac ablations include bleeding, cardiac tamponade, stroke/TIA, pulmonary vein stenosis, phrenic nerve injury, thromboembolism, air embolism, post-procedural arrhythmias, and vascular complications. Further, recurrences of atrial fibrillation (AF) or atrial tachycardia after an initial AF catheter ablation procedure (20 – 40% of patients) are common.

Gelsomino 2014 noted in a study of SAEs (Serious Adverse Event) rates for studies of convergent AF ablation (N=335) (**Table 1**). There were 3 early deaths (0.9%) and three conversions to sternotomy and cardiopulmonary bypass (0.9%). There were no late deaths or thromboembolic events. These SAE rates include both catheter ablation and surgical ablation procedures in the reviewed studies. Expected adverse event rates from an isolated surgical procedure are likely to be lower.

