### 5.3.2 Secondary Safety Endpoint

1. The proportion of subjects reporting one or more device- or procedure-related SAEs, as assessed at 30 days, 75 days, 90 days, 6 months and 12 months of follow-up.
2. The proportion of subjects with stroke or TIA through 12 months
3. The proportion of subjects with major bleeding related to anticoagulation treatment through 12 months
4. The proportion of subjects requiring cardioversion through 12 months
5. The proportion of subjects requiring an arrhythmia-related hospitalization through 12 months

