#### 6.1.1 Potential Adverse Events

The following anticipated adverse events have been identified as possible complications of percutaneous atrial fibrillation ablation procedures and these and others may be associated with the FARAPULSE Endocardial Ablation System:

- Access site complications (e.g., hematoma, pseudo-aneurysm)
- Air embolism
- Anemia
- Arrhythmia, potentially requiring cardioversion, defibrillation, or rhythm management device
- Arteriovenous fistulae
- Back pain
- Bed sores
- Bleeding, hematoma, hemorrhage or aneurysm at vascular access sites
- Blood pressure changes including hypotension or hypertension
- Coronary artery or vein injury
- Cardiac tamponade
- Cardiac arrest or cardiac failure
- Catheter entrapment
- Cardiogenic shock
- Conduction system injury resulting in sinus arrest or heart block, either transient or permanent
- Congestive heart failure
- Death
- Drug allergic reaction or side effects (e.g., from contrast, steroids, analgesics, anesthetics, anticoagulants, sedatives, etc.)
- Esophageal injury, ulcer or fistula
- Hemorrhage
- Hemodynamic compromise
- Hemopericardium
- Hemoperitoneum

- Hemothorax
- Local infection, systemic infection, and/or sepsis
- Myocardial infarction / transient ischemia
- Nerve damage
- Organ failure
- Pain
- Perforation (e.g., of diaphragm, heart, liver, lung, and/or vessels).
- Pericardial irritation
- Pericardial effusion
- Pericarditis
- Peritonitis
- Phrenic nerve injury
- Pneumomediastinum
- Pneumopericardium
- Pneumoperitoneum
- Pneumothorax
- Pulmonary vein injury or stenosis
- Risk of cancer or birth defect/harm to fetus from x-ray exposure
- Skin burns/irritation from x-ray exposure
- Stroke/transient ischemic attack
- Surgical or open-heart surgery to remove retained catheter
- Thrombosis
- Thromboembolism
- Vessel damage, dissection, or occlusion.

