### *Serious Adverse Event (SAE):*

- led to death,
- led to serious deterioration in the health of the subject, that either resulted in:
  - a life-threatening illness or injury, or
  - a permanent impairment of a body structure or a body function, or
  - in-patient or prolonged hospitalization, or
  - medical or surgical intervention to prevent life-threatening illness or injury or permanent impairment to a body structure or a body function.

- led to fetal distress, fetal death or a congenital abnormality or birth defect.

NOTE: Planned hospitalization for a pre-existing condition, or a procedure required by the CIP, without serious deterioration in health, is not considered a serious adverse event.

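### Does limiting the composite's only embolic row to clot let a serious air embolism escape the primary safety rate?

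*Combined protocol and SAP*

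**What the plan says.** The Composite Safety Endpoint (synopsis, sections 5.3.1 and 7.6.1) lists ten early-onset and two late-onset serious adverse events, counted when related to the device or procedure. Air embolism is not among them. Table 3 defines the thromboembolism row as "Formation in a blood vessel of a clot (thrombus) that results from the breaking loose of all or part of an existing thrombus".

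Three other definitions matter:

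- **Serious adverse event (section 8.1).** One way to qualify is "medical or surgical intervention to prevent life-threatening illness or injury or permanent impairment to a body structure or a body function". This sits under the requirement that the event led to a serious deterioration in the subject's health.
- **Vascular access (Table 3).** "Vascular access complication (e.g. groin hematoma, AV fistula, pseudoaneurysm) requiring intervention (e.g. surgical repair, blood transfusion) or admission or prolonged hospitalization".
- **Myocardial infarction (Table 3).** One of three sufficient criteria is "imaging evidence of new loss of viable myocardium or new regional wall motion abnormality", with no minimum duration.

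The protocol treats air embolism as a distinct and expected complication. Section 3.5 names "thromboembolism, air embolism, post-procedural arrhythmias, and vascular complications" among the most common ones. Section 6.1.1 lists it apart from thromboembolism and adds that "these and others may be associated with the FARAPULSE Endocardial Ablation System". Section 3.4.1 reports from this same study: "One patient was treated for an air embolism during the index procedure".

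Secondary safety endpoint 1 (section 5.3.2) is "The proportion of subjects reporting one or more device- or procedure-related SAEs". Section 10.10 has the CEC adjudicate every procedure-related or serious event and has the DSMB review safety data at least after every twentieth enrolment.

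**The concern.** A reader who follows an air embolism through the composite finds that the obvious row excludes it by definition. The row with an intervention criterion, vascular access, gives only access-site injuries as examples. Nothing sends air embolism there, and nothing keeps it out. The CEC has no written scoring rule, yet the event has already occurred in this study.

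Two things would be at stake. A related, serious, treated harm could be missing from the headline safety rate, or two similar events could be classified differently. Section 7.2 justifies the sample size by the event-rate estimates and confidence intervals it allows, and says the data will inform the powering of a later pilot study. A primary rate that is low for a definitional reason would carry forward.

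**Working it through.** **1. Trace through the twelve rows.** Take an air embolism that is related, and serious only because intervention was needed.

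| Row | Does it score? |
|---|---|
| Death; stroke/TIA; myocardial infarction | Only through that consequence. Table 3 does not restrict the cause to clot. |
| Hospitalization | Yes, if there is a new admission or a longer stay. No minimum length is set. |
| Thromboembolism | No: clot only. |
| Vascular access complication | Has an intervention criterion, but the examples are access-site lesions. |
| Diaphragmatic paralysis, pericarditis, tamponade/perforation, heart block, PV stenosis, atrio-esophageal fistula | No: different events. |

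No row clearly captures it. To be missed, an event must meet all of these conditions: related; a serious deterioration; intervention of the kind section 8.1 describes; no death; no neurological event; no infarction under Table 3; no admission or longer stay.

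**2. The known case.** Section 3.4.1 says that the subject was treated, that the event resolved, and that all 16 were discharged in good condition. It does not give seriousness, relatedness or length of stay. Treatment alone does not meet section 8.1, so a missed case is not shown.

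**3. Size.** The plan gives no expected composite rate, performance goal or test, so there is no figure to reproduce. It names no interval method either; I assume exact (Clopper-Pearson) 95% limits. For x events in n subjects:

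- lower limit = 2.5% quantile of Beta(x, n − x + 1), or 0 if x = 0
- upper limit = 97.5% quantile of Beta(x + 1, n − x); for x = 0 this is 1 − 0.025^(1/n)

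Inputs: n = 16 (section 3.4.1) and n = 80 (section 5.4, assuming all 80 are treated). One subject is worth 100/80 = 1.25 points at n = 80 and 100/16 = 6.25 points at n = 16.

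| Events/n | Rate | Exact 95% interval |
|---|---|---|
| 0/16 | 0% | 0 to 20.59% |
| 1/16 | 6.25% | 0.16 to 30.23% |
| 0/80 | 0% | 0 to 4.51% |
| 1/80 | 1.25% | 0.03 to 6.77% |
| 2/80 | 2.50% | 0.30 to 8.74% |
| 3/80 | 3.75% | 0.78 to 10.57% |
| 5/80 | 6.25% | 2.06 to 13.99% |

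Leaving out a sole event lowers the upper limit by 6.77 − 4.51 = 2.26 points. With two other composite events (assumed), the comparison is 2/80 against 3/80. As an extreme, suppose treated air embolism continued at 1 in 16, giving 80 × 1/16 = 5 cases, and that all were related, serious through intervention alone, and otherwise unscored. The comparison would then be 0/80 against 5/80. The documents support none of those suppositions.

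**4. What secondary endpoint 1 does.** Every composite event is a related serious adverse event. Reading the 12-month assessment as cumulative, with the same denominator, the 12-month proportion for endpoint 1 cannot be below the composite proportion. The gap between them is the share of subjects whose related serious events all fall outside the composite. A sole unscored air embolism would show as 0/80 beside 1/80.

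**The case for a change.** The best argument for acting is the composite's own logic. The vascular access, tamponade and heart block rows can all score on intervention without an admission, so a treated air embolism is the same kind of harm with no row. It has occurred here, so the CEC may need a rule for a case already on file. Secondary endpoint 1 pools all related serious events and does not name the type. A written rule seems cheap: adverse events are already recorded at the procedure (section 5.12.2) and adjudicated (section 10.10).

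What stands is that the rule is unwritten. The rest is weaker. Section 6.1.1 lists dozens of anticipated events, and others, such as pneumothorax, hemothorax and catheter entrapment, have no row either. Nothing says the composite should cover all embolic or all anticipated events. Naming air embolism apart from thromboembolism agrees with a clot definition. On a plain reading, an air embolism scores through its consequences.

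The available amendments gain little. A note keeping air embolism out of the vascular access row would narrow the primary endpoint, in the favourable direction, after a known event. A supplementary composite adding air embolism would be built around one observed case and would say little beyond endpoint 1 and an ordinary listing of related serious events by type. Either might also need ethics committee and competent authority approval under section 11.3.

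**Conclusion.** No change to the plan is needed. Table 3 leaves a narrow scoring question that an adjudication committee would ordinarily settle and record, applying one reading to every subject. Followed exactly as written, the plan still records a related serious air embolism, sends it to the CEC and counts it in secondary safety endpoint 1.

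The effect is confined to the primary composite: 1.25 percentage points per affected subject at n = 80, and possibly zero to date. Section 7.1 specifies descriptive analysis without a hypothesis test, and the documents state no safety goal, so no conclusion becomes unsound.

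This rests on three assumptions: all 80 subjects are treated; endpoint 1 is reported cumulatively to 12 months; and the CEC treats like cases alike. It would need another look if several such events occurred and the composite were quoted alone, without endpoint 1, as the safety input to the pilot study.

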## 5.3 Study Endpoints

### 5.3.1 Primary Safety Endpoint

The primary safety endpoint for this study is the Composite Safety Endpoint (CSE) defined as the incidence of the following early-onset and late-onset serious adverse events (SAEs) which are device- or procedure-related:

Early onset (within 30 days of any endocardial ablation for atrial fibrillation)

- Death
- Myocardial infarction (MI)
- Persistent diaphragmatic paralysis
- Stroke or transient ischemic attack (TIA)
- Peripheral or organ thromboembolism
- Pericarditis
- Cardiac tamponade / perforation
- Vascular access complications
- Hospitalization (initial or prolonged)\*
- Heart block

Late onset (any time during follow-up)

- Pulmonary vein (PV) stenosis (> 70% diameter reduction from baseline)
- Atrio-esophageal fistula

\* Excludes hospitalization (initial & prolonged) solely due to arrhythmia (AF/Atrial Flutter/Atrial Tachycardia) recurrence or due to non-urgent cardioversion (pharmacological or electrical). Hospitalization excludes visits to hospital-associated outpatient facilities such as clinics or emergency wards.

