## 7.6 Assessment of Safety

### 7.6.1 Primary Safety Endpoint

The primary safety endpoint for this study is the Composite Safety Endpoint (CSE) defined as the incidence of the following early-onset and late-onset serious adverse events (SAEs) which are device- or procedure-related:

Early onset (within 30 days of any endocardial ablation for atrial fibrillation)

- Death
- Myocardial infarction (MI)
- Persistent diaphragmatic paralysis
- Stroke or transient ischemic attack (TIA)
- Peripheral or organ thromboembolism
- Pericarditis
- Cardiac tamponade / perforation
- Vascular access complications
- Hospitalization (initial or prolonged)\*
- Heart block

Late onset (any time during follow-up)

- Pulmonary vein (PV) stenosis (> 70% diameter reduction from baseline)
- Atrio-esophageal fistula

\* Excludes hospitalization (initial & prolonged) solely due to arrhythmia (AF/Atrial Flutter/Atrial Tachycardia) recurrence or due to non-urgent cardioversion (pharmacological or electrical). Hospitalization excludes visits to hospital-associated outpatient facilities such as clinics or emergency wards.

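### Table 3 ties the heart-block component to undefined inappropriate ablation, so some related serious block can be missed by the primary safety composite

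*Combined protocol and SAP*

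**What the plan says.** Section 5.3.1 defines the primary safety endpoint as a composite of "early-onset and late-onset serious adverse events (SAEs) which are device- or procedure-related". Heart block is in the early group, whose window is "Early onset (within 30 days of any endocardial ablation for atrial fibrillation"). The Executive Summary and section 7.6.1 repeat the list. In all three places the item is simply heart block, with no qualifier.

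Table 3 gives the working definition: "Impairment of AV conduction requiring intervention due to inappropriate ablation application".

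Three other provisions matter:

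- The composite has a separate hospitalization component. Its footnote says what it leaves out: "Excludes hospitalization (initial & prolonged) solely due to arrhythmia (AF/Atrial Flutter/Atrial Tachycardia) recurrence or due to non-urgent cardioversion". It also leaves out outpatient and emergency-ward visits. Heart block is not among the exclusions.
- Section 6.1.1 lists as an anticipated risk "Conduction system injury resulting in sinus arrest or heart block, either transient or permanent". It says nothing about how the device was used.
- Secondary safety endpoint 1 in section 5.3.2 is "The proportion of subjects reporting one or more device- or procedure-related SAEs", again whatever the manner of use.

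**The concern.** The composite asks a causality question: did the device or procedure bring about this serious event? The heart-block row also asks whether the ablation was applied inappropriately. On its plain reading that is a question of fault. AV block after an ablation delivered as instructed would then fail the row, although it is a risk of the device itself, which a safety and feasibility study sets out to describe.

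The main product of this study is a set of event rates with confidence intervals. Section 7.2 says they will inform dosage, procedural requirements and the powering of a later pilot study. An error in this row can only remove events, so it runs in the reassuring direction. The Clinical Events Committee in section 10.10 is given no standard for judging what is inappropriate, so two adjudicators could classify the same event differently.

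**Working it through.** The plan states no heart-block rate, no expected composite rate and no performance goal, so there is no planned figure to reproduce. The check is mainly a comparison of text.

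**1. Compare the two conditions.** Section 5.3.1 requires "serious adverse events (SAEs) which are device- or procedure-related". Table 3 requires AV impairment, an intervention, and inappropriate ablation as the cause. An event must pass both, so the heart-block row is narrower than the composite's own test. No other Table 3 row depends on how the device was used.

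**2. Compare with the rest of the protocol.** In section 8.1 an adverse device effect includes events from use error but is not limited to them. In the causality scale, error in use is one possible sign of a causal relationship, and the criteria need not all be met. The row is therefore out of line with the protocol's own approach to relatedness.

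**3. Trace a related, serious block after correct use, within 30 days, read literally.**

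| What happens | Heart-block row | Hospitalization component | Primary composite | Secondary safety endpoint 1 |
|---|---|---|---|---|
| Causes admission or prolongs the stay | Not met | Met | Counted, but not as heart block | Counted |
| Needs intervention, no admission or longer stay | Not met | Not met | Missed, unless another component is met | Counted |

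The second row of the table can occur. Under section 8.1 an event can be serious because intervention was needed to prevent life-threatening illness or permanent impairment, without any hospitalization. Section 5.12.2 places a pacing catheter in the right ventricle for the procedure, so block managed in the procedure room is plausible.

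**4. A smaller gap.** The row requires ablation as the cause. Block caused by catheter manipulation would be procedure-related and pass the composite's test, yet fail the row.

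**5. Size, for illustration.** Input: N = 80, the maximum in section 5.4. Assumptions: all 80 are evaluable and there is no other composite event.

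- One subject: 1/80 = 1.25 percentage points.
- Clopper-Pearson 95% interval for 0/80: upper limit 1 − 0.025^(1/80) = 4.5%, so 0 to 4.5%.
- For 1/80 = 1.25%: lower limit 1 − 0.975^(1/80) = 0.03%; upper limit is the 0.975 quantile of Beta(2, 79) = 6.8%.
- For 2/80 = 2.5%: 0.3 to 8.7%.

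**6. How often it might arise.** The documents give no rate, so a range is assumed. The chance of at least one related serious block among 80 subjects is 1 − (1 − p)^80: 33% at p = 0.5%, 55% at p = 1% and 80% at p = 2%. Only some of these would need intervention without affecting hospitalization, so the chance of a missed event is lower by an unknown amount.

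**The case against.** A reader might infer that heart block after correct use is shut out of the primary safety endpoint altogether. The documents do not support that. Block that causes admission or prolongs the stay within 30 days enters through the hospitalization component, whose exclusions do not mention it. Investigators must report all adverse events (section 8.2), the Clinical Events Committee and the Data and Safety Monitoring Board review safety (section 10.10), and secondary safety endpoint 1 counts every related serious event. The risk is not hidden.

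A reader might also take the row as a rule that counts only misuse. That is not established either. The protocol's lesions are aimed at the pulmonary veins, with optional isthmus or additional lesions, and none is meant to interrupt AV conduction. *Inappropriate* could therefore mean energy reaching tissue it was not meant for, which is a causal attribution and not a judgement of fault.

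Nor do the documents show that the rate will in fact be understated. That needs a related serious block with no effect on hospitalization and no other component met, and a committee that adopts the misuse reading. The study is descriptive (section 7.1), so no test or sample size depends on the answer.

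All of this stands, and it narrows the point without removing it. A secondary endpoint does not correct the primary one. Block captured as hospitalization would not appear as heart block in a breakdown by component. That two readings are available is itself a defect in an endpoint definition.

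**Conclusion.** The point holds in a limited form. The heart-block row carries an undefined condition that is stricter than the composite's relatedness test. On the literal reading, the primary composite misses related serious block after correct use that needs intervention but neither causes nor prolongs hospitalization and meets no other component. Block captured through hospitalization is counted but loses its label. On the alternative reading the definition is still ambiguous.

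The contrast between 0/80 and 1/80 is conditional on the stated assumptions and is not a prediction. The possible distortion is small in absolute terms, 1.25 points per subject at N = 80, but it goes in one direction only and falls on a safety estimate meant to guide the next study. The correction is worth making because it is nearly free and helps under either reading.

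**What to change.** In Table 3, delete the closing clause of the heart-block row that attributes the event to inappropriate application, so that the row ends after the word intervention. The composite's existing requirement, a serious event related to the device or procedure, then decides causality. This brings Table 3 into line with sections 5.3.1 and 7.6.1.

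Do not add the word *new* to the row. It could exclude worsening of AV impairment that was already present.

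Apply the revised row to every subject, including the 16 that section 3.4.1 reports as already enrolled at Prague. The events are already collected, so no new data are needed.

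The cost is a small protocol amendment. Section 11.3 requires Ethics Committee and Competent Authority approval for significant changes that may affect the validity of the data, so approval may be needed. Deleting a condition can add events but cannot remove any, so the reported safety rate can only stay the same or become slightly less favourable.
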